Our study coordinator, study physicians, physical therapists, PI ([name]), and research collaborators recruited subjects using a variety of strategies shown effective in the past. First, the team identified potential subjects using Institutional Review Board (IRB) approved resources to inform persons with SCI that are currently admitted to inpatient rehabilitation/outpatient units of Spaulding Rehabilitation Hospital, Boston University Medical Center, Massachusetts General Hospital, Gaylord hospital, Albany Medical Center, and Maine Medical Center. Subjects also will be recruited by word of mouth and flyers at these facilities. Eligible subjects screened at INSPIRE Laboratory, Spaulding Rehabilitation Hospital Cambridge, MA. At the screening visit, subjects informed of this project, their potential involvement, the possible benefits, and risks, and their right to terminate participation at any time without penalty. Qualifying subjects in agreement with the study details asked to sign the informed consent and HIPAA form approved by Partners IRB. All potential subjects entered the study according to the inclusion/exclusion criteria above and following medical clearance. Experiments will be conducted at the Spaulding Rehabilitation Hospitals.

11. Interventions

- a. Intervention Procedures: This placebo-controlled study will examine the combined effects of caffeine (vs. placebo) and AIH (vs. SHAM) on walking performance in persons with chronic, iSCI. Participants will receive three combinatorial interventions in random order: placebo+AIH, caffeine+AIH, caffeine+SHAM. The order of interventions will be block randomized. The initial screening and evaluation procedures are similar for all participants. For each intervention, participants will complete up to 8 visits/intervention (1 baseline/intervention + 5 treatment days/intervention + 2 follow-up days/intervention). Participants will complete a total of 24 visits (8 visits/intervention x 3 interventions) after the initial screen. Participant enrollment and allocation will be completed during the screening visit. Baseline will be recorded up to 3 days prior to the first intervention.

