Participants will be randomized to a sequence of three interventions (Table 1). Participants will participate in a single-day screening and 24 visits (1 baseline/intervention + 5 treatment days/intervention + 2 follow-up days/intervention). Participant enrollment and allocation will be completed during the screening visit. Baseline visits will occur up to 3 days prior to the first treatment. A two-week washout will follow the last treatment day. This washout duration is more conservative than washout durations reported in previous animal and human intermittent hypoxia studies.^{53, 54}

DETAILED STUDY PROTOCOL

Table 1. Timing Schedule for enrollment, interventions, and assessments

Timepoints (days)	Enrollment		Baseline			Intervention			Follow-ups/Washout	
	-5	0	1	2	3	4	5	8	14	
Screening and Allocation Timing										
Eligibility screen	x									
Informed consent	x									
Medical clearance	x									
Allocation		x								
Drug script		x								
Intervention Timing										
Placebo+AIH			x	x	x	x	x			
Caffeine+AIH			x	x	x	x	x			
Caffeine+SHAM			x	x	x	x	x			
Assessment Timing										
Primary outcome										
• Walking speed (10MWT, s)		x					x	x	x	
Other outcomes										
• Voluntary leg strength		x					x	x	x	
• Spasticity		x					x	x	x	
• Spasm frequency		x					x	x	x	
• Walking function		x					x	x	x	
• Walking distance (6MWT, m)		x					x	x	x	
• Walking Balance (TUG, s)		x					x	x	x	
• Blinding Questionnaire			x	x	x	x	x			
• Weight (kg)		x						x	x	
Safety Outcomes										
• Pain (0-10)		x	x	x	x	x	x	x	x	
• Blood pressure (mmHg)		x	x	x	x	x	x	x	x	
• Heart rate (BPM)		x	x	x	x	x	x	x	x	
• Oxygen saturation (%)		x	x	x	x	x	x	x	x	
• Memory (0-30)		x	x	x	x	x	x	x	x	
Biomarkers										
• CYP1A2 Polymorphism		x								
• Caffeine serum level (mg/L)			x				x			
• Inflammation (CRP)			x				x			

DETAILED STUDY PROTOCOL

14. Sample size

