All data will be managed using REDCap⁶⁵, MS 365 Excel 16.54 (Microsoft, USA), and MATLAB R2020a (Mathworks Inc, USA) and will be analyzed using SPSS[®] Statistics 26 (64-bit edition, IBM, USA). Descriptive statistics, including means, standard deviations and 95% confidence intervals of the within-participant pre-post change for each intervention will be calculated for all measures. The baseline characteristics of the participants will be compared using parametric and non-parametric inferencing.

Hypothesis testing: To evaluate our main hypothesis that caffeine prior to AIH enhances walking recovery, we will perform a linear mixed model with fixed effects at a significance at the p=0.05 level.⁶⁶ Intervention (caffeine+dAIH, caffeine+SHAM, placebo+dAIH) and time (day) will be the fixed main effects, with subject as random effect and walking speed (10MWT) as repeat measures. Differences from BL will be compared between and within interventions at D₅, F₁, and F₂. Bonferroni corrections will be made for multiple comparisons. If distributions are not normal, we will perform comparable nonparametric tests. If baseline measures are significantly different between sessions (interventions), an analysis of co-variance (ANCOVA) will be used to analyze the data. We predict walking speed (10MWT) will be greater after daily caffeine+AIH as compared to after daily placebo+AIH and daily caffeine+SHAM.

Blinding integrity analysis: we plan to rigorously quantify blinding integrity here. We will ask participants and raters to guess the intervention received at the end of each intervention and indicate guess confidence using a Likert scale.^{67,68} We will use a contingency table and Fischer's

DETAILED STUDY PROTOCOL

Exact Test to determine if the probability of correct guessing is different from chance. Using multivariate logistic regressions, we also will assess factors that may influence guessing (i.e., adverse events, perceived effects, and sensorimotor changes). In the event of a medical emergency, we will unblind the PI, study participants, and care provider. We also will notify IRB of treatment allocation during adverse event reporting as necessary.

V. Monitoring

21. Data monitoring

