- Concealment mechanism – We will conceal the intervention allocation from the evaluators performing the assessments, treatment administrators, and the study participant.
- Implementation – The PI and biostatistician will generate the allocation sequences for the cross-over study. The trial coordinator will enroll participants and study staff who are not training or assessing the participants will assign the block randomized interventions.

11. Sample size

Twenty individuals with chronic (> 6 months post injury), motor-incomplete SCI (i.e., American Spinal Injury Association Impairment Scale (AIS) C or D) will be recruited for the study. Prior to the start of this clinical trial, we estimated the number of participants needed to achieve study objectives. In particular, our sample size computation focused on treatments: caffeine+dAIH versus placebo+dAIH alone. Our preliminary study on the effects of caffeine prior to single AIH sequence (vs placebo+SHAM) on 10MWT showed a decrease of 2.4s±1.2s. Under the hypothesis of an additive effect of caffeine+dAIH (vs. placebo+dAIH), we anticipate the difference in walking speed (10MWT time) change between treatments would be approximately 0.06m/s. With N=20 cross-over participants (includes 17% attrition rate), a repeated measures ANOVA comparing 4 treatments across 4 time points, using pooled SD of 1.3s across days, will be sensitive to detect a difference at power of $1 - \beta = 0.80$ ($f=0.7$, $F_{3,12}=3.5$; $p=0.4$, $\alpha=.05$).

12. Framework

This placebo-controlled study will examine the combined effects of caffeine and AIH results in greater walking performance than either intervention alone. However, this trial will not evaluate the potential superiority or equivalence of caffeine+AIH to standard of care treatments for persons with chronic iSCI.

13. Statistical interim analyses and stopping guidance

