• Blinding Questionnaire		x	x	x	x	x			
• Weight (kg)	x						x	x	
Safety Outcomes									
• Pain (0-10)	x	x	x	x	x	x	x	x	
• Blood pressure (mmHg)	x	x	x	x	x	x	x	x	
• Heart rate (BPM)	x	x	x	x	x	x	x	x	
• Oxygen saturation (%)	x	x	x	x	x	x	x	x	
• Memory (0-30)	x	x	x	x	x	x	x	x	
Biomarkers									
• CYP1A2 Polymorphism	x								
• Caffeine serum level (mg/L)		x				x			
• Inflammation (CRP)		x			x		x		

IV. Statistical Principles

We plan to use a parametric linear mixed model since this method is sensitive to within subject changes and robust against variability, small sample sizes, and missing/unbalanced data sets as compared to other statistical models.²⁶ If the results do not meet these model assumptions, we will apply alternative non-parametric tests.

16. Level of significance

All applicable statistical tests will be 2-sided and will be performed using a 5% significance level.

17. Adjustment for multiplicity

we do not plan to adjust for multiplicity.

18. Confidence intervals

Statistical comparisons will include 95% (2-sided) confidence intervals (CIs).

19. Adherence and protocol deviations

We will record a deviation (if the even does not significantly affect a participant's rights, safety, or well-being, or trial outcomes), or a violation (if the deviation may potentially significantly impact the completeness, accuracy, and/or reliability of the trial data or that may significantly affect a patient's rights, safety, or well-being). All protocol deviations/violations will be logged, but no formal statistical testing will be performed.

Adverse events will be reported on an IRB-approved electronic Case Report Form (eCRF). Details will include the type of event, date of onset, duration, intensity, causality relationship to the study drug(s), and outcome. If an adverse event should occur, every attempt will be made to obtain as much information as possible about event evaluation and outcome. If a serious adverse event occurs, the treatment will be interrupted or discontinued at the physician investigator's discretion. All protocol deviations will be reported to the PI ([name]) and the IRB.

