Alternative statistical methods: If distributions are not normal, we will perform comparable nonparametric tests. If baseline measures are significantly different between sessions (interventions), an analysis of co-variance (ANCOVA) will be used to analyze the data.

Blinding integrity analysis: we plan to rigorously quantify blinding integrity here. We will ask participants and raters to guess the intervention received at the end of each intervention and indicate guess confidence using a Likert scale.^{38,39} We will use a contingency table and Fischer's Exact Test to determine if the probability of correct guessing is different from chance. Using multivariate logistic regressions, we also will assess factors that may influence guessing (i.e., adverse events, perceived effects, and sensorimotor changes). In the event of a medical emergency, we will unblind the PI, study participants, and care provider. We also will notify IRB of treatment allocation during adverse event reporting as necessary.

CYP1A2 analysis: we will perform subgroup analysis on our study cohort to determine the extent to which differences in caffeine metabolism due to CYP1A2 polymorphisms may affect responsiveness to the combinatorial treatment of caffeine+AIH.

28. Missing data

Rigorous efforts will be made to ensure complete outcome data. However, we anticipate that participants in this study cohort may be unable to complete the study requirements. Missing data will be reported and documented as we did in our previous clinical trial.⁴⁰ We will document reasons for missing data and our approach to handle missing data during statistical analysis. We will account for potential outliers in our results using a conservative outlier labeling technique set forth by Hoaglin and Tukey.⁴¹

29. Additional analyses

We do not anticipate any additional statistical analyses methods.

30. Harms

Checklists and note pages are used to log any deviations or omissions from the protocols. Any clinical/health related issues would be immediately presented to the subject to determine appropriate notification (i.e., current physician or appropriate specialist). Based on the seriousness of the situation Drs. [name] or [name] may be contacted to provide clinical guidance on the appropriate course of action as per our Laboratory Medical Emergency Safety Plan.

31. Statistical software

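### The planned Fisher's exact test cannot reliably say whether blinding guesses differ from chance: guesses are linked within participants, and the test measures association, not a correct-guess rate

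*Combined protocol and SAP*

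**What the plan says.** Protocol section 20 and SAP section 27 describe the same blinding analysis. They will ask "participants and raters to guess the intervention received at the end of each intervention and indicate guess confidence using a Likert scale". The test is then stated in one sentence, as a contingency table with Fisher's "Exact Test to determine if the probability of correct guessing is different from chance". Logistic regressions on factors that may influence guessing follow, with no subject or rater term mentioned.

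The design in protocol section 11 is a three-period crossover: "Participants will receive three combinatorial interventions in random order: placebo+AIH, caffeine+AIH, caffeine+SHAM". A completer therefore supplies three guesses. Protocol section 17 says that participants and evaluators know which air mixtures and caffeine interventions are possible, but not the combination delivered. It also reports that some participants in the team's prior study were uncertain of what they had received.

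Table 1 in the protocol marks the "Blinding Questionnaire" on all five treatment days, whereas the text asks for one guess when each intervention ends. The plan does not give the table layout, the chance value, whether guesses are pooled or tested by period, how uncertain answers count, or how repeated guesses by one person are handled.

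**The concern.** Two features of the named test do not fit its stated purpose.

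- **Independence.** A participant who has already named one intervention may avoid naming it again, or may give the same answer every time. Either habit links the three guesses. Fisher's test takes each entry in the table as a separate observation. The primary 10MWT model has a random subject effect; the blinding analysis has no counterpart.
- **Question asked.** The stated aim compares a rate of correct guessing with chance. Fisher's test asks whether the row and column classifications are associated. Depending on what the rows and columns are, that can be a different question.

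The outcome is a walk at the fastest safe speed, so it depends on effort and possibly on expectation. Readers will use the blinding result to judge how far to trust a 20-person crossover. An unstated layout also leaves room to choose, after the data are seen, between tables that can give opposite answers.

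**Working it through.** **Inputs.** The plan states "With N=20 cross-over participants (includes 17% attrition rate"), so 20 x 0.83 = 16.6, or about 17 completers; 16 is the value rounded down. At three guesses each this is 60 guesses, or 51 for 17 completers. The level is 5%, two-sided (SAP section 16). The documents give no figure for the blinding test, so there is none to reproduce. A chance level of 1/3 and the guessing behaviours below are assumptions.

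**Step 1: correct guesses per person when guesses carry no information.**

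- Each label used once: of the six possible matchings with the true order, two give 0 correct, three give 1 and one gives 3. The mean is 3/6 + 3/6 = 1, and the variance is (3/6 x 1 + 1/6 x 9) - 1 = 1.
- Independent guesses: variance 3 x 1/3 x 2/3 = 0.67.
- One guess repeated: always exactly 1 correct, variance 0.

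For 20 people the variance of the total correct is 20.0, 13.3 or 0.

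**Step 2: size of a pooled 3x3 guess-by-actual Fisher test at nominal 5%.** Simulation with treatment order randomised within person:

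| Guessing behaviour | N = 20 | 17 completers |
|---|---|---|
| Each label used once | 0.168 | 0.161 |
| Independent guesses | 0.058 | 0.049 |
| Half the people repeat one guess | 0.001 | 0.002 |
| Everyone repeats one guess | 0.000 | 0.000 |

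The first row used 20,000 runs and the others 3,000 (Monte Carlo standard error at 5%: 0.0015 and 0.004). With 16 participants and each label used once the size is 0.15.

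The two extremes can be checked by hand. If everyone repeats one guess, each person adds one count to every actual intervention under the same label. The rows are then identical and the test can never reject. If each label is used once and N = 20, every cell has expectation 20 x 1/3 = 6.67 and variance 20 x 2/9 = 4.44. The expected Pearson chi-square is then 9 x 4.44/6.67 = 6, against a nominal 4, an inflation of 1.5. The 5% critical value on 4 degrees of freedom, 9.488, acts like 9.488/1.5 = 6.325. Its tail is exp(-3.163) x (1 + 3.163) = 0.176, close to the simulated 0.168.

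**Step 3: testing one period at a time.** With one guess per person and N = 20, the simulated size is 0.046, which is acceptable.

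**Step 4: association against agreement.**

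- Correct/incorrect by intervention, 16 of 20 correct in each: the rates are equal, so Fisher p = 1.0 for any pair of interventions, although 48/60 = 80% are correct.
- The same 80% in a guess-by-actual table with errors spread evenly: p = 1.3e-11, so unblinding is detected.
- 30 of 60 correct with errors spread evenly: guess-by-actual Fisher p = 0.14. The exact within-person distribution from step 1 (each label used once) gives an upper tail of 0.0217, below 0.025.
- Everyone right on one intervention and swapping the other two: agreement is 20/60 = 1/3, and Fisher p = 1e-26.

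**Step 5: a plain binomial test is not the remedy.** At N = 20 its upper critical value is 28 of 60 (nominal tail 0.0219). If each label is used once, the true tail is 0.0527, and the within-person critical value is 30.

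**The case against.** The strongest reply is that the plan never says the guesses are pooled. That is correct: pooling is read from the mention of a single contingency table, and a per-period test would hold its size (step 3). Splitting by period still leaves the layout and the chance value undefined.

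Second, a reader might take 0.17 as the false-alarm rate of the planned test. The documents do not support that. It requires pooling and every participant using each label exactly once. Nothing says how the question is posed, and uncertain answers, which occurred in the prior study, would break that pattern. With independent guesses the pooled test is close to nominal.

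Third, the label-swap table may look like a false positive for Fisher's test. It is not. People who swap two labels consistently can tell the interventions apart, so masking has failed and the association is real. A statistic based only on total correct would miss it, which limits the proposed replacement as well. In a guess-by-actual table, uninformative guessing implies both no association and chance agreement, and strong ordinary unblinding is found.

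Finally, this is a supporting analysis. No exclusion or decision rule depends on it, and guess confidence and the logistic regressions add evidence. All of this stands. It narrows the point without removing it, because the named test still matches neither the stated aim nor the crossover structure.

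**Conclusion.** The concern holds in a limited form. Fisher's exact test does not assess a correct-guess rate against chance, and the plan makes no provision for three linked guesses per completer. If the guesses are pooled in a guess-by-actual table, the true size lies anywhere from about 0 to about 0.17 at nominal 5%, in a direction set by guessing style. In a correct/incorrect-by-intervention table, uniform unblinding can go unseen.

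The range rests on assumed guessing behaviours, 16 to 20 participants and, for rates against chance, a level of 1/3. That level would change if the questionnaire asked about caffeine and air mixture separately: two of the three interventions contain caffeine, so always answering caffeine would be right 2/3 of the time.

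A reader might go further and infer that the blinding verdict will be wrong, or that the walking result is compromised. Neither follows. The layout and guessing behaviour are unknown, and the primary 10MWT analysis does not use the blinding test. The point deserves correction before unblinding but is secondary to the primary analysis.

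**What to change.** Replace the Fisher test in protocol section 20 and SAP section 27 with a within-participant permutation test.

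- **Statistic and reference.** Count correct end-of-intervention guesses. Hold the guesses fixed and permute each person's actual interventions over the orders that the randomisation allows, which the SAP should list.
- **Dropouts.** Permute over completed periods only. Someone with one completed period then adds nothing to the test.
- **Reporting.** Give the full guess-by-actual table and the percent correct per intervention, with participant-clustered confidence intervals, so that systematic label swaps are visible.
- **Raters.** Analyse them separately, with intervals that allow for one rater guessing for several participants. Add subject and rater terms to the logistic regressions.
- **Definitions.** State how the question is worded, the chance level that follows, and how uncertain answers count.
- **Timing.** Reconcile Table 1 (all five treatment days) with the text (end of each intervention), and say which guess is analysed.

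The cost is SAP wording and a few lines of code; no new data are needed.
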